5.2.6 Treatment Compliance

Not Applicable.

5.3 Data Analysis General Considerations

Because of the crossover design of the study, analyses results will be summarized by treatment sequence (Sequence 1 to Sequence 6) and by treatment group (Placebo, E2730 40 mg, E2730 120 mg) as appropriate. When results are summarized by treatment, data from subjects receiving a given treatment in the corresponding period are combined. For example, placebo treatment comprises data from Treatment Period 1 of Sequence 1, Treatment Period 3 of Sequence 2, Treatment Period 2 of Sequence 3, Treatment Period 1 of Sequence 4, Treatment Period 2 of Sequence 5, and Treatment Period 3 of Sequence 6 (see [Table of Treatment Sequences](#)).

For those listings or data summaries where change from baseline measurements will be calculated and presented, unless stated otherwise, the last observed measurement, including unscheduled assessments, prior to the first dose of study drug in the first period will be considered the baseline measurement for all assessments except PPR related endpoints.

All descriptive statistics for continuous variables will be reported using number of observations (n), mean, standard deviation (SD), median, minimum, and maximum unless otherwise specified. Categorical variables will be summarized as number and percentage of subjects.

Listings will include all subjects, unless specified otherwise, and will be presented by sequence, treatment and subject.

5.3.1 Pooling of Centers

Subjects from all centers will be pooled for all analyses.

5.3.2 Adjustments for Covariates

Predose PPR value as baseline will be included in the mixed model as the adjustment for covariate.

5.3.3 Multiple Comparisons/Multiplicity

Not applicable.

5.3.4 Examination of Subgroups

Not applicable.

5.3.5 Handling of Missing Data, Dropouts, and Outliers

If there are more than 3 dropouts in the study, a subject discontinuing/discontinued from the study for any reason may be replaced at the discretion of the sponsor. Missing values in PPR will not be imputed in this study.

For PD analyses, two summaries for the primary and secondary PPR endpoints will be produced, if different, one for all data in PD analysis set and one for all completers.

For safety summaries, all data in Safety Analysis Set will be included.

5.3.6 Other Considerations

Not applicable.

5.4 Efficacy Analyses

Not Applicable.

5.5 Pharmacokinetic, Pharmacodynamic, CC1 Analyses

5.5.1 Pharmacokinetic Analyses

The Safety Analysis Set will be used for individual E2730 and M1 plasma concentration-time listings. The PK Analysis set will be used for summaries of E2730 and M1 plasma concentrations, summaries and listings of PK parameters. Plasma concentrations will be tabulated by nominal sampling time and summarized by treatment dose using summary statistics.

The following PK parameters will be derived by noncompartmental analysis using plasma concentrations of E2730 and M1. These parameters will include, but are not limited to:

- C_{\max} maximum observed concentration
- $AUC_{(0-8h)}$ area under concentration x time curve from time 0 to 8 hours postdose
- t_{\max} time to reach C_{\max} following drug administration

The PK of E2730 will be analyzed based on available data from this study. The PK and PD Analysis datasets will be used to evaluate the relationship of PK of E2730 and change in PPR response. The PK-PD analyses may include the examination of the relationship of PK of E2730 and PPR response (eg, time of onset, maximum change, and duration of PPR; Bond and Lader data) using model-based approaches.

5.5.2 Pharmacodynamic Analyses

The following PD analyses will be performed on the PD Analysis Set.

No multiplicity adjustments will be made. The 5 PPR measured postdose on a treatment day will be averaged and used for both primary endpoint and secondary endpoints. The predose PPR data from the respective treatment period will be used as the baseline data for that period.

Primary PD Analyses

The primary endpoint of mean change from baseline of the average PPR for each E2730 dose compared with placebo in the most sensitive eye condition will be performed using a mixed effects model for crossover study. The model will include treatment, period, and sequence as fixed effects, baseline (predose) measurement as a covariate, and subject nested within sequence as a random effect. Where data are normally distributed, least squares (LS) means, difference in LS means of each E2730 dose compared to placebo, and 90% CIs will be presented with no adjustments for multiplicity.

Secondary PD Analyses

The secondary endpoints of mean change from baseline of the average PPR for each E2730 dose compared with placebo in all 3 different eye conditions (eye closure, eyes closed, and eyes open) will be analyzed and summarized by using the same mixed effects model as for primary PD analyses.

Additional analysis by graphical exploration on onset, maximum change, and duration of photosensitivity response at each dose level will be performed for all 3 eye conditions at the time course of E2730 as compared to placebo. This analysis will provide further information on the frequency and percentage of subjects with Complete Suppression, Partial Response, and No Response of PPR (see [Section 8.3 Definitions of Derived PPR Variables](#)) at each dose level of E2730 as compared to placebo.

Sensitivity analyses for PPR may be conducted, for example, of PPR for subjects who completed all Treatment Periods 1-3 versus those who are included in the PD Analysis Set.

CCI

5.6 Safety Analyses

Evaluations of safety will be performed on the Safety Analysis Set. Safety data that will be evaluated include adverse events (AEs), clinical laboratory results, vital signs, ECGs, C-SSRS, and neurological/physical examinations. Treatment-emergent adverse events (TEAEs) will be summarized by presenting for each treatment group, the incidence of AEs.

Descriptive summary statistics (eg, mean, SD, median, minimum, and maximum for continuous variables, and the number and percent for categorical variables) of the laboratory, vital signs, and ECG parameters, and changes from baseline will be evaluated by treatment group. The proportion of subjects with any treatment-emergent report of suicidal ideation and behavior and intensity of these behaviors will be summarized.

All safety data will be presented in listings. Study Day 1 for all safety analyses will be defined as the date of the dose of study drug in treatment period 1.

5.6.1 Extent of Exposure

The number of subjects exposed to each study drug dose and placebo will be summarized descriptively by treatment and treatment period and provided in a listing.

5.6.2 Adverse Events

The AE verbatim descriptions (investigator terms from the CRF) will be classified into standardized medical terminology using the Medical Dictionary for Regulatory Activities (MedDRA). AEs will be coded to the MedDRA (Version 20.0 or higher) lower level term (LLT) closest to the verbatim term. The linked MedDRA PT and primary system organ class (SOC) are also captured in the database.

A TEAE is defined as an AE that emerges during treatment, having been absent at pretreatment (Baseline) or

- Reemerges during treatment, having been present at pretreatment (Baseline) but stopped before treatment, or
- Worsens in severity during treatment relative to the pretreatment state, when the AE is continuous.

Only those AEs that are treatment-emergent will be included in summary tables. All AEs, treatment-emergent or otherwise, will be presented in subject data listings.

The TEAEs will be summarized by treatment group, using the Safety Analysis Set. The incidence of TEAEs will be reported as the number (percentage) of subjects with TEAEs by SOC and PT. A subject will be counted only once within an SOC and PT, even if the subject experienced more than 1 TEAE within a specific SOC and PT. The number (percentage) of

subjects with TEAEs will also be summarized by maximum severity (mild, moderate, or severe). The number (percentage) of subjects with TEAEs will also be summarized by relationship to study drug (Yes [related] or No [not related]).

The number (percentage) of patients with treatment-emergent SAEs will be summarized by the latest edition of MedDRA SOC, and PT. A subject data listing of all SAEs, including deaths, will be provided.

A subject data listing of all AEs leading to discontinuation from study drug will be provided.

5.6.3 Laboratory Values

Laboratory results will be summarized using Système International (SI) units, as appropriate. For all quantitative parameters listed in [protocol section 9.5.1.5.3](#), the actual value and the change from baseline to each postbaseline visit and to the end of treatment (defined as the last on-treatment value) will be summarized by visit and treatment group using descriptive statistics. Qualitative parameters listed in [protocol section 9.5.1.5.3](#) will be summarized using frequencies (number and percentage of subjects), and changes from baseline to each postbaseline visit and to end of treatment will be reported using shift tables. Percentages will be based on the number of subjects with both nonmissing baseline and relevant postbaseline results.

Laboratory test results will be assigned a low/normal/high (LNH) classification according to whether the value was below (L), within (N), or above (H) the laboratory parameter's reference range. Within-treatment comparisons for each laboratory parameter will be based on 3-by-3 tables (shift tables) that compare the baseline LNH classification to the LNH classification at each postbaseline visit and at the end of treatment.

[Appendix 1](#) (Sponsor's Grading for Laboratory Values) below presents the criteria that will be used to identify subjects with treatment-emergent markedly abnormal laboratory values (TEMAVs). Except for phosphate, a TEMA V is defined as a postbaseline value with an increase from baseline to a grade of 2 or higher. For phosphate, a TEMA V was defined as a postbaseline value with an increase from baseline to a grade of 3 or higher. When displaying the incidence of TEMA Vs, each subject may be counted once in the laboratory parameter high and in the laboratory parameter low categories, as applicable.

5.6.4 Vital Signs

Descriptive statistics for vital signs parameters (ie, systolic and diastolic BP, pulse, respiratory rate, and temperature) and changes from baseline will be presented by visit and treatment group.

Clinically notable ranges are defined as follows.

Variable	Criterion value ^a	Change relative to baseline ^a
Heart rate	>120 bpm	Increase of ≥ 15 bpm

	<50 bpm	Decrease of ≥ 15 bpm
Systolic BP	>180 mmHg	Increase of ≥ 20 mmHg
	<90 mmHg	Decrease of ≥ 20 mmHg
Diastolic BP	>105 mmHg	Increase of ≥ 15 mmHg
	<50 mmHg	Decrease of ≥ 15 mmHg

^a Clinically notable means that a value must have met both the criterion value and satisfied the magnitude of change relative to baseline.

Vital sign values will be listed on an individual basis by sequence, treatment and subject. Clinically notable vital sign values will be identified on the listings as those above (H) or below (L) a clinically notable range.

5.6.5 Electrocardiograms

Descriptive statistics for ECG parameters and changes from baseline will be presented by visit and treatment group.

Shift tables will present changes from baseline in ECG interpretation (categorized as normal; abnormal, not clinically significant; and abnormal, clinically significant) to end of treatment.

In addition, the number (percentage) of subjects with at least 1 postbaseline abnormal ECG result in QTc Fridericia during the treatment period will be summarized. Clinically abnormal ECG results in QTc Fridericia will be categorized as follows:

For the QT interval assessment, clinically abnormal ECG results for QT interval corrected for heart rate using Fridericia's formula (QTcF) will be categorized as follows: QTcF values >450 msec, >480 msec, and >500 msec, and time-matched change from baseline in QTcF >30 msec and >60 msec.

5.6.6 Other Safety Analyses

The results of C-SSRS assessments will be listed for each subject. The incidence of suicidal ideation or suicidal behavior will be summarized by treatment group as appropriate.

5.7 Other Analyses

Not applicable.

6 INTERIM ANALYSES

No formal interim analyses are planned for this study.

7 CHANGES IN THE PLANNED ANALYSES

There are no changes to the statistical methods in this analysis plan compared to the latest protocol. Any future changes to the analysis will be documented separately and will be addressed in the Clinical Study Report.

8 DEFINITIONS AND CONVENTIONS FOR DATA HANDLING

8.1 Definitions of Baseline Values

For PPR analyses in all 3 treatment periods, the predose PPR data from the respective treatment period will be used as baseline data for that period. If predose PPR data is not valid, the average PPR value at screening visit will be used as baseline for PPR analyses.

The baseline value for all safety endpoints will be the last non-missing measurement occurring prior to the first dose of study drug in the treatment period 1.

8.2 Definitions of Treatment Periods

Treatment periods 1 to 3 are one-day treatment periods which will include single dose of study drug on Day 1 (Visit 2) for treatment period 1, Day 22 (Visit 3) for treatment period 2, and Day 43 (Visit 4) for treatment period 3.

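### If dosing-day labs are predose only, the SAP reports Visit 3 and 4 labs under the treatment about to be given, or under none, so the lab tables do not compare E2730 with placebo

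*SAP*

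**What the plan says.** SAP 8.2 defines the periods: "Treatment periods 1 to 3 are one-day treatment periods which will include single dose of study drug", on Days 1, 22 and 43. SAP 5.3 states that for summaries by treatment "data from subjects receiving a given treatment in the corresponding period are combined". Under SAP 8.1 the safety baseline "will be the last non-missing measurement occurring prior to the first dose of study drug in the treatment period 1", so any lab, ECG or vital sign taken before the dose at Visit 3 or 4 counts as postbaseline.

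The safety summaries use these definitions:

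- **Labs (SAP 5.6.3).** The rule for quantitative labs, covering each postbaseline visit and an end of treatment, closes with "defined as the last on-treatment value) will be summarized by visit and treatment group".
- **Vital signs (SAP 5.6.4).** Descriptive statistics "and changes from baseline will be presented by visit and treatment group".
- **ECG (SAP 5.6.5).** "Descriptive statistics for ECG parameters and changes from baseline will be presented by visit and treatment group". A separate count covers subjects with "at least 1 postbaseline abnormal ECG result in QTc Fridericia during the treatment period will be summarized"; that sentence does not say whether the count is split by treatment.
- **Adverse events (SAP 5.6.2).** "A TEAE is defined as an AE that emerges during treatment, having been absent at pretreatment (Baseline"). TEAEs are tabulated by treatment group, but no window ties an event to a dose.

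On timing, protocol Table 5 marks laboratory tests at Screening, Visits 2, 3 and 4, and Follow-up. Footnote g lists the panels and gives no clock time. The synopsis and protocol 9.4.5 and 9.4.7.2 allow a snack half an hour before dosing, once the laboratory blood has been drawn. By contrast, footnotes c and e give explicit predose and postdose times for vital signs and ECGs.

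**The concern.** SAP 5.1.2 lists as a secondary endpoint the changes in vital signs, chemistry, blood counts and liver tests following single doses of E2730, against placebo. A lab drawn before the dose at Visit 3 or 4 can only reflect what was given about three weeks earlier. Filed under that day's treatment, it describes a dose the subject has not yet taken. An abnormal liver test after 120 mg could then appear in the placebo column, and with about 9 subjects one such value is visible in the table.

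The SAP does address this for medications: 5.2.5 assigns a concomitant medication to a dose until 28 days or the next dose date, whichever comes first. It has no matching rule for labs or adverse events.

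**Working it through.** The plan gives no figure on this point to reproduce, so the check is an enumeration.

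**Inputs.** The six sequences (protocol Table 3, SAP 3.2): ABC, BCA, CAB, ACB, BAC, CBA, with A placebo, B 40 mg and C 120 mg. One subject is taken per sequence and only scheduled samples are counted. Two assumptions: (i) dosing-day labs are predose only; (ii) the one-day period covers the whole visit. Support for (ii) is that SAP 8.1 treats predose PPR as data of that day's period, but that sentence concerns PPR only.

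**Step 1: label against last dose.** The label is the treatment of that day's period; the last dose is that of the previous period.

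| Sequence | Visit 3 label / last dose | Visit 4 label / last dose | Visit 5 label / last dose |
|---|---|---|---|
| ABC | B / A | C / B | none / C |
| BCA | C / B | A / C | none / A |
| CAB | A / C | B / A | none / B |
| ACB | C / A | B / C | none / B |
| BAC | A / B | C / A | none / C |
| CBA | B / C | A / B | none / A |

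- Visits 3 and 4: 6 × 2 = 12 cells, 0 matches. No sequence repeats a treatment, so a match is impossible.
- Placebo-labelled cells: 4 (BCA Visit 4 and CAB Visit 3, after 120 mg; BAC Visit 3 and CBA Visit 4, after 40 mg). All 4 follow E2730.
- Post-placebo samples: 6. Four are labelled E2730 (ABC and ACB at Visit 3, CAB and BAC at Visit 4), two (BCA and CBA at Visit 5) have no label, and none is labelled placebo.
- All scheduled postbaseline labs: 12 + 6 = 18, of which 0 carry the last dose received.

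**Step 2: drop assumption (ii).** If the period starts at dosing, the 12 Visit 3/4 labs fall in no period. With the 6 Follow-up labs, 18 of 18 are unlabelled. This is a gap rather than a wrong label, but still no lab is tied to the dose it follows.

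**Step 3: drop assumption (i).** If a postdose lab is also drawn on dosing days, that sample is labelled correctly and only the predose one is affected.

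**Step 4: predose ECGs and vital signs, per subject.** Here the predose times are stated.

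- ECG, postbaseline: Visit 2, 1; Visit 3, 2; Visit 4, 2; Visit 5, 1. Total 6, of which 2 are predose (33%).
- Vital-sign time points: 5 + 6 + 6 + 1 = 18, of which 2 are predose (11%).

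**Step 5: residual drug.** Assuming terminal decay at the half-lives in protocol Table 1 (59.0 to 69.8 h; none is given for 120 mg) and 18 to 24 days between doses, the fraction left is 2^(−t/half-life). The extremes are 2^(−432/69.8) = 1.37% and 2^(−576/59.0) = 0.12%.

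**Step 6: adverse event follow-up.** Protocol 9.5.1.5.1 collects events through the last visit and for 5 half-lives of 71.2 h: 5 × 71.2 = 356 h = 14.8 days. The starting point of the 5 half-lives is not stated. Counted from Follow-up (18 to 24 days after the last dose), collection ends at 32.8 to 38.8 days. Counted from the last dose, the half-lives end at 14.8 days, before Follow-up. Periods 1 and 2 each last only 18 to 24 days.

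**The case against.** The strongest reply is that predose-only timing is not established. The snack wording shows that a predose blood draw exists, not that there is no other, and it says nothing about urinalysis. Other text fits a postdose draw better: the secondary endpoint speaks of changes following doses, SAP 5.6.3 refers to a last on-treatment value, and protocol 9.7.1.8.3 plans shifts to the highest and lowest value during the treatment period. The laboratory manual might settle the time. This stands as a reason to keep the point conditional. None of that text schedules a postdose lab, however, while the same table gives postdose times for ECGs and vital signs.

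Second, table shells and derivation rules (SAP 9 and 11) are separate documents and could show rows marked predose under each treatment without breaching 5.3. For ECGs and vital signs this largely answers the point. A reader might infer that those tables are bound to be wrong too; the documents do not show that, because the predose times are explicit, postdose readings exist, and SAP 5.6.5 already uses time-matched QTcF changes. For labs, a predose marker would stop the table misleading, but would still not tie any lab to the dose it follows.

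Third, all safety data are listed (SAP 5.6), and listings are by sequence, treatment and subject (SAP 5.3), so the preceding dose can be recovered. That stands and limits the severity.

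**Conclusion.** The point holds conditionally. If dosing-day labs are predose only, the SAP as written ties no scheduled postbaseline lab to the dose it follows: 12 of 18 are labelled with a treatment not yet given and 6 have no label, or all 18 have no label if the period starts at dosing. Either way the by-treatment lab tables do not deliver the comparison with placebo named in SAP 5.1.2. Both the draw time and the whole-day period are inferences.

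A reader might infer more than this. The documents do not establish that the lab tables will certainly be mislabelled, since an unlisted postdose draw is possible. Nor is this carryover: under the decay assumption only about 0.1 to 1.4% of concentration remains at the next dose. The primary PD analysis has its own per-period baseline and postdose average and is unaffected.

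Severity is minor to moderate: descriptive safety tables for about 9 subjects, with full listings.

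**What to change.** 1. State the dosing-day laboratory draw time, for blood and urine, and whether any draw is postdose.
2. Keep SAP 8.2 for PD and add a safety attribution rule: each lab, by actual sampling time, belongs to the most recent dose received, up to just before the next dose. Visit 3 predose labs then go to Period 1, Visit 4 predose labs to Period 2, and Follow-up labs to Period 3, shown as values about 3 weeks after dosing. Each treatment then has 4 cells from Visits 3 and 4 and 2 from Follow-up. The Period 1 safety baseline can stay.
3. Show Visit 3 and 4 predose ECGs and vital signs as predose rows. Do not count them as postdose results of that day's treatment, including in any QTcF count by treatment.
4. State an adverse event window from each dose to the next. For Period 3, show events beyond a comparable window of about 3 weeks separately, so that follow-up length does not differ by treatment: about 9 subjects cannot balance evenly over six sequences. State where the 5 half-lives start.

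Items 2 to 4 cost SAP wording and programming, apart from the half-life starting point, which is protocol text. Item 1 is a short clarification in the protocol or laboratory manual. No new data are needed. The limit is that relabelling does not supply labs near peak exposure: median tmax in protocol Table 1 is 3.00 h at 40 mg and 4.50 h at 120 mg, and these samples are about three weeks later.

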8.3 Definitions of Derived PPR Variables

The followings are definitions for PPR related analyses:

- Standard Photosensitivity Response (SPR): a standardized derived measure of the range of frequencies of IPS that elicits epileptiform EEG responses in a subject. The range is assigned a number, representing the number of frequency steps, from 0 to 14 between the lowest to the highest frequencies of IPS that elicits epileptiform activity by EEG. If the upper and lower limit of measured frequencies is the same, SPR will be set = 1.
- Most sensitive eye condition: SPR is measured in each of 3 eye states: eye closure, eyes closed, and eyes open. That eye condition that yields the largest SPR before dosing is defined as the most sensitive eye condition.
- Duration of suppression: The difference in hours between the onset of suppression and the end of suppression of photosensitivity. The onset of suppression is defined as the first time point at which the SPR was at least 3 units below the mean SPR at baseline. The end of suppression is defined as the last time (second time) with two successive reductions in SPR of at least 3 units lower than the mean SPR at baseline.
- Complete suppression is defined as a standardized photosensitivity response (SPR) reduction to 0 over at least 1 time point for all three eye conditions. Partial response is defined as a reduction in SPR of at least 3 units from baseline for at least 3 time points, and no time points with at least 3 units of increase, in the most sensitive eye condition; without meeting the complete suppression definition. No response is

defined as the response not meeting complete suppression or partial suppression definitions.

